## **3. Subjects**

### **a. Description of study populations**

The participants in our study are healthy volunteers. Parents and their children between the ages of 6 months to 12 years of age will be invited to participate. All children will need consent from their parent or legal guardian, and children over the age of 4 will need to provide assent. Our accrual ceiling is 360 parent-child dyads (720 participants total). If participants withdraw, they will be replaced.

### **b. Inclusion criteria**

All children between the ages of 6 months to 12 years of age who are *typically developing* and born of a full term pregnancy if under 24 months of age, healthy, and English speaking are eligible for inclusion in the study. *Typically developing* children would not have any diagnosed congenital conditions, developmental delay or disability, dyslexia, PDD, ADD, ADHD, or ASD. In addition, we will only enroll subjects if they are from a racial and ethnic group that is still needed to ensure the diversity and representative nature of our sample as set forth in the Planned Enrollment Form. These are the initial screening criteria that will be used.

#### **c. Exclusion criteria**

If the participants do not meet the inclusion criteria, they will not be included in the study. Children who are deaf or blind will also need to be excluded from the study. The Eligibility Checklist will be used by investigators at the time of screening for admission to the protocol and will list the inclusion criteria to determine the dyad's eligibility.

While we want to make this study as inclusive as possible, our goal is to understand toy play for typical American children in the time allotted by the CPSC using only the resources allocated in our budget. Thus, the following bullet points explain why the following populations must be excluded from our study:

- *Children outside of the 6 month-12 year age range:* These years cover early life and are the ages of interest for children's play and are of central significance to the Consumer Product Safety Commission's goals.
- *Families not fluent in English:* Fluency in English is essential for parents to be able to fill out surveys. Families also need to be fluent in English so that they can comprehend verbal directions given by the experimenter during the testing session. If we included people who were not fluent in English, we would need many additional staff members who speak the multitude of languages of the diverse population of the Washington, D.C metro area to work with participants during the testing session and code the videos after the testing session is complete.
- *Children who are sick, not typically developing, born premature (if they are under 24 months of age), blind, or deaf:* We must recruit a healthy sample of typically developing children born in a full term pregnancy (if they are under 24 months of age) who are not blind or deaf for this project to remove any potential confounds that atypical conditions may have on children's play. *Typically developing* children would not have any diagnosed congenital conditions, developmental delay or disability, dyslexia, PDD, ADD, ADHD, or ASD. Including other populations such as deaf or blind children would require a different experimental set up, stimulus toys, and resources (i.e., someone who could convert our surveys to American Sign Language or Braille and could code the videos for the parent child behaviors during those sessions).

- *Children who are not adding to the ethnic and racial diversity of the sample:* The goal of our study is to recruit a sample of subjects who are racially and ethnically diverse. By making this diverse sample a priority, we hope that our results will be applicable to the diverse populations residing within the United States. To keep with this goal of a diverse and representative sample of children, we may have to exclude some families if we have already reached the quota of families from that particular racial or ethnic group.

#### **4. Study Design and Methods**

##### **a. Study overview**

Participants will be children aged 6 months to 12 years and their parents. Participants will receive children's products or toys to play with during an hour play session. Based on the manufacturer's suggested age, some products will be geared towards children who are younger, some will be geared toward children their own age, and others will be aimed at older children. Each child will first play alone and then play with a parent. Different sets of toys will be presented when children switch from playing alone to playing in a dyad. The play sessions will be videorecorded. Video records will subsequently be scored for children's play with the toys.

Participation in this project will take roughly 1-2 hours for the play session of the visit and approximately 1 additional hour for the parent to complete accompanying relevant questionnaires, which can be done at home. Participation in the study requires one visit to the CFRS lab.

This research is social and behavioral in nature, and the visits are considered outpatient. Participants will be tested at the CFRS laboratory in Bethesda, MD.

Subjects who participate in this study are not required to participate in other protocols.

##### **b. Recruitment**

Subjects will be recruited through the following methods:

(1) Birth records: We will purchase lists of local addresses and phone numbers of families with children. This recruitment procedure has been used in CFRS studies previously approved by the NICHD IRB (Study # 88-CH-0032; Study # 02-CH-0278). If we have only the family's mailing address, a short letter or postcard describing the study will be mailed to each family, with an invitation to call or email the lab to learn more. If the family's telephone number is available, we also may directly call families, provide a short description of the study, and ask if they would like to participate in the project.

(2) The local community: We will contact authorized personnel in the community and ask for permission to post or circulate information. We may contact:

- Newspapers, magazines, local community publications
  - A short blurb of information with the CFRS contact information would be printed.
- Neighborhood listservs, blogs, and online parenting communities on social networking sites such as Facebook
  - A short blurb of information with the CFRS contact information would be posted.
- Schools, child care centers, and after-school programs
  - Directors may post flyers or place informational flyers or brochures in children's backpacks or mailboxes to take home to their parents.
- Coffee shops, libraries, recreation centers, and other places known to attract parents and their children.
  - Flyers with detachable CFRS contact information tabs would be posted.

(3) Prior participants in CFRS studies: Families who have previously participated in other approved CFRS studies (e.g., 04-CH-0250, 03-CH-0069) and have provided their phone numbers will be re-contacted with information about this new study and will be recruited for participation.

(4) NIH websites and recruitment hubs: Those reading about the study on the Clinical Center website, the Clinical Center Facebook or Twitter, the OPR Listserv, the Clinical Center Newsletter, ClinicalTrials.gov, ResearchMatch, and the CFRS website and who contact the CFRS or the Clinical Center with interest in the study will be considered for participation.

We anticipate that we will be able to recruit at a rate of 5 children per week.

### **Screening**

We plan to have a telephone conversation with parents who express interest in the study. During the call, the study will be explained in detail, and parents will be encouraged to ask questions. For those who wish to participate, we will conduct a short interview to check their eligibility criteria (see the Intake Criteria checklist). Parents who are eligible and interested in the study will receive the Informed Consent Form and surveys in the mail in paper format, which they will fill out and return to CFRS staff. Surveys and consent forms may also be completed electronically on the Clinical Trials Survey System (CTSS).

#### **c. Study procedures**

##### **Procedure**

Participants will be 720 parents and their children from 6 months to 12 years of age. We will recruit children divided into the following six age groups:

- 6-11 mos

- 12-18 mos (1-1.5 years)
- 19-35 mos (1.5-2 years)
- 36-71 mos (3-5 years)
- 72-107 mos (6-8 years)
- 108-144 mos (9-12 years)

Each child will first :

- Play alone
- then*
- Play with parent

Each child in each age group will receive children's products and toys from 6 of the 9 following categories:

- (1) Construction toys (e.g., blocks, interlocking building materials)
- (2) Exploratory toys (e.g., clay, sand toys)
- (3) Games & Puzzles
- (4) Instructional toys (e.g., books, science kits)
- (5) Sports, Recreational, & Outdoor Equipment
- (6) Imaginative play toys (e.g., puppets, dolls, dress up materials)
- (7) Small Wheeled Vehicles (e.g., car toys)
- (8) Arts & Crafts toys
- (9) Musical toys (e.g., musical instruments)

- Prior to testing, all toys used in this project will be inspected for safety hazards by staff trained in conducting safety evaluations of toys for the Consumer Product Safety Commission. Toys will be inspected for small parts, mechanical hazards (cord length, magnet strength, etc.), lead, and phthalates. All small parts will be removed from toys for children under age 3, and toys will be replaced with similar ones if any mechanical hazards, lead, or phthalates are identified.
- There is a large body of research regarding children's gravitation towards and play with sex-stereotyped toys (O'Brien & Huston, 1985; Caldera et al., 1989). Although child gender is an important factor to consider when studying the qualities of toys, the current study will use gender neutral toys as stimuli in an attempt to eliminate any potential gender confound.

The experimenters will select three representative target toys from each toy category. Target ages are determined by the manufacturer's suggested age.

- Children will be presented with one of three (counterbalanced) toys targeted for their age group from 6 of the 9 toy categories.
- When presented, each target toy will be paired with two additional toys from the same toy category: one targeted to the age group just below and one from the age group just above the target toy.

- Children will receive novel sets of toys when switching from playing alone to play with parent.

To decrease the burden on parents and their children, reduce unplanned missingness, and increase data quality, we are using a 3-form planned missingness design. Because of this design, parents and their children will only have to play with toys from 6 of the 9 categories.

Parents and their children will be offered to take a break from playing approximately every 15 minutes during the toy play session in the event that they are tired of playing with the toys. In addition, to ease frustration that can occur when transitioning from one toy type to the next, we will give children and their parents a couple of minutes notice before the transition occurs.

All play sessions will be video recorded.

### **Measures and Surveys:**

The following questionnaires will be sent to the parent to complete before the scheduled visit with the child. Parents can bring these documents with them to the scheduled visit or return them by mail. Although the surveys are currently in paper format, for ease of completion, we may convert them to electronic format that parents can fill out online through CTSS. These questionnaires include the following:

- Consent form and permission to use videorecorded data.
- Basic demographics about the child/family/home life, measuring: Number/ages of children at home, birth order, parental age, parental education, parental marital status, race/ethnicity, etc. (see Bornstein et al., 1996).
- Hollingshead Four-Factor Index of Social Status (Hollingshead, 1975): Measures SES of the family.
- Vineland Adaptive Behavior Scales (VABS; Sparrow, Balla, & Cicchetti, 1984): Measures the child's developmental level in a more sensitive way than by the rough proxy of age
- Temperament through the use of validated scales for different age groups: Infant Behavior Questionnaire (IBQ), Early Childhood Behavior Questionnaire (ECBQ), Children's Behavior Questionnaire (CBQ), Temperament in Middle Childhood Questionnaire (TMCQ), Early Adolescent Temperament Questionnaire (EATQ) (see Bornstein et al., 2015; Rothbart, 2007).
- Social Desirability Scale, Short Form (Reynolds, 1982): A questionnaire used during self-reporting to detect and control for possible social desirability bias.
- Knowledge of Infant Development Inventory (KIDI) for children  $< 2$ ; or the Knowledge of Effective Parenting Scale (KEPS) for children  $\geq 2$ : The KIDI has been previously approved by the IRB in CFRS protocol (Study# 88-CH-0032; Study # 02-CH-0278). The KIDI and the KEPS are designed to assess knowledge of parental practices, developmental processes, and infant norms, areas that form a knowledge base that may influence and regulate parental behavior vis-a-vis an

individual child (MacPhee, 1981; Morawska, Sanders, & Winter, 2007). The KIDI is appropriate for use with parents with children up to 2 years old and the instrument is comprised of 75 items covering four areas: Norms and Milestones, Principles (developmental processes), Parenting (strategies), and Health and Safety (guidelines). The KEPS is appropriate for use with parents with children as young as 2 years old and is comprised of 28 items covering four areas: Promoting Development, Principles of Effective Parenting, Using Assertive Discipline, and Causes of Behavior Problems.

- Knowledge of Play (see Tamis-LeMonda et al., 1994): A questionnaire used to assess parent's knowledge of children's play, specifically, what types of play behaviors are more complex than others.
- Parent Toy Questionnaire (PTQ): Uses some new and some similar questions from a previous (2002) CPSC-sponsored study of toy play. Parents would be asked: "Where do you get information about toys? Where do you buy your toys? What information do you gather about toys before purchasing them? What is some information you wish that you had before purchasing toys?
  - **Optional parent focus group:** If time and resources permit, we may invite a small number of parents to participate in a focus group conversation about toys.
    - The PTQ will ask parents to check a box if they are interested in this focus group opportunity. We will only contact parents who have checked this box.
    - Topics discussed in the focus group will elaborate on the topics highlighted on the PTQ. The focus group will give parents an opportunity to elaborate verbally on their thoughts about age appropriateness of children's toys and how they make their toy purchasing decisions. This mixed methods research can supplement the quantitative data that parents provide in the PTQ.
    - The focus group may take place at the CFRS or we may use a phone conference call for ease of scheduling.

The following questionnaires will be completed at the end of the testing session.

- Perceptions of child's comfort during testing situation, as reported by (1) the parent and (2) the experimenter (Bornstein et al., 1999).
- Questions adapted from the Home Observation for Measurement of the Environment Inventory (HOME; see Linver, Brooks-Gunn, Cabrera, 2004) to gather information about what toys are already at the child's home and in the child's play environment.
- Additional questions about the toys and their features, including the toys that the child played with during the testing session and additional toys of interest to the CFRS and the CPSC.

Child questions

- For children over the age of 4, we will ask children questions to assess what they thought of each toy by asking: “How much did you like [toy]? Why?” Children will respond to scaled items by pointing to a visual representation of a Likert-type scale in the form of smiley faces (adapted from Harter, 1982; Richards & Calvert, 2015).
- We will also ask the child whether or not she/he has played with the toys before.

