### **b. Secondary outcome measures**

Our other secondary outcome measures include the following:

- Parts and features of toys used by the child
- Duration of time child spends with each toy
- Child preference for the toys based on child-report (smiley face Likert scale)
- Number of times and duration of time the child solicits the parent's or friend's involvement during play

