## **10. Statistical Analysis**

### **a. Analysis of data/ study outcomes**

For our primary outcome measure, our independent variables will be the age group for which the toy is aimed (younger vs. age-appropriate vs. older; within-subject) and the age group of the child (6 groups; between-subject), and our dependent variables will be the video-coded measures of play. The statistical methodology that we will use to analyze this question is a repeated-measures ANCOVA with up to five covariates. Our five covariates include the following: (1) toy characteristics, (2) child temperament, (3) family socioeconomic status, (4) child preferences for the toy, and (5) parenting knowledge.

For our secondary outcome of interest (how children play alone vs. with parent), we will conduct another repeated-measures ANCOVA with condition (alone vs. with parent) and designated toy age (younger vs. age-appropriate vs. older) as within-subject factors and child age (6 groups) as a between-subject factor. Again, our dependent variables will be the video-coded measures of play. We will also use the same five covariates mentioned above: (1) toy characteristics, (2) child temperament, (3) family socioeconomic status, (4) child preferences for the toys, and (5) parenting knowledge.

Both of the repeated-measures ANCOVA designs will also be employed when we examine the dependent variables of secondary interest noted in section 9b, such as parts and features of toys used by the child, duration of time child spends with each toy, child preference for the toys based on child-report (smiley face Likert scale), and the number of times and duration of time the child solicits the parent's involvement during play. The independent variables mentioned above would remain the same.

We do not have any planned interim analysis. Our criteria for significance is alpha = .05. Due to the protocol's design, unplanned missingness will be low. Missing data procedures, such as Full Information Maximum Likelihood and Multiple Imputation, will be used.

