**b. Consent procedures**

Permission for participation of minors will be obtained from parents/legal guardians. Parents will have the opportunity to carefully review the written consent form and ask questions regarding the study prior to signing. After the consent form has been filled out and parental permission is obtained, the parent and child may begin participation in the study.

Permission from only one parent is being requested. The permission of one parent is sufficient for compliance with 45 CFR 46.404, as the proposed research poses risk no greater than that ordinarily encountered in daily life or during the performance of routine physical or psychological examinations or tests (i.e., minimal risk).

At the time of the play session, CFRS staff will also obtain assent from the children to ensure that they want to participate in the study as well. Parents will be present during the assent process and will sign the bottom of the assent form to certify that they witnessed their child's assent.

Children between the ages of 4-5 will provide verbal assent. Researchers will sign the form to certify that they received assent from the participant. Language for verbal assent will be as follows:

"We are doing this project because we want to know more about how kids play with toys. If you join in, you will play with some toys. My friend here is going to use a camera to make a video of you while you play with the toys. Nobody will see the video except people who work with us, and we will keep the video private by putting it in a locked room. Then, I will ask you some questions. You might like playing with these toys, but you might not like it. If you do not want to play with them, you do not have to. We will get to learn about what kids like and how they think if you will help us. You will also get to play with some toys. If you do not want to play anymore, you do not have to. Just tell me if you do not want to play anymore! If you decide you want to stop, you can leave—I will not be upset. Anything that you say to me will be safe. Do you have any questions? Would you like to do this?"

Children over the age of 6 will be read the same statement and will be asked to sign a written assent form to indicate their willingness to participate.

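### Child preference for the toys is rated after the play and is itself an outcome, yet sections 10a and 10b use it as a covariate for that play

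*Combined protocol and SAP*

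**What the plan says.** **As a covariate.** The primary model in section 10a is a repeated-measures ANCOVA of video-coded play, with toy age (three levels, within child) and child age group (six, between children). Its covariate list ends "4) child preferences for the toy, and (5) parenting knowledge". The second model adds alone versus with parent as a within-child factor and uses the same five covariates. Section 10b repeats the list for both questions and bases the power statement on five covariates.

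**As an outcome.** Section 9b lists "Child preference for the toys based on child-report (smiley face Likert scale" among the secondary outcomes. Section 10a applies both ANCOVA designs to the 9b outcomes.

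**How it is measured.** Section 4c says "For children over the age of 4, we will ask children questions to assess what they thought of each toy", using the question "How much did you like [toy]? Why". This comes under its own sub-heading, Child questions, directly after the list opened by "The following questionnaires will be completed at the end of the testing session". The sub-heading gives no time of its own. The assent script in section 14b first describes the play and then says "Then, I will ask you some questions".

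**Order of play.** Section 4a: "Each child will first play alone and then play with a parent". The toys differ between the two phases, so each rating belongs to one phase.

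**The concern.** The primary objective (section 2a) asks how play differs between a toy meant for the child's age and toys of the same category meant for the adjacent ages. Part of that difference may come about because children like a well-matched toy more, or like it more because they played well with it. A covariate that can itself respond to toy age, or to the play, changes the question: the model then compares toys at equal liking and does not give the total toy-age difference. The age categorisation that feeds the revised guidelines rests on the total difference.

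Two further matters follow from the same item. Read literally, preference would be a covariate in the model where it is the dependent variable. And if liking is asked at the end of the session, the alone-versus-parent contrast on preference also reflects how long ago the toy was used.

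**Working it through.** The plan gives no figure on this point, so there is nothing to reproduce. Steps 1, 4 and 5 use the documents alone, apart from an assumed even spread of ages in step 5. The effect sizes in steps 2, 3 and 7 and the phase lengths in step 6 are assumed.

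**1. Order of events.** Toy age is set when the toy is presented, play is then recorded, and liking is asked afterwards. This holds whether the rating comes after each toy, at the switch of phase or at the end. The covariate problem therefore does not depend on the end-of-session timing.

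**2. Entered per toy, with toy age affecting liking.** Let D be the toy-age difference in complexity, d the difference in liking between the same toys, and g the change in complexity per liking point. The adjusted difference is D − g × d. Assume D = 1 level in favour of the age-appropriate toy over the older toy, a 1-point liking difference, and g from 0.1 to 0.5.
- Age-appropriate toy liked more (d = +1): 1 − 0.1 = 0.9 down to 1 − 0.5 = 0.5.
- Older toy liked more (d = −1): 1 + 0.1 = 1.1 up to 1 + 0.5 = 1.5.

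The sign of the bias depends on whether liking and complexity move together across toy ages.

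**3. Entered per toy, with liking resulting from the play.** Take liking = b × play + noise, unit standard deviations, and a true toy-age effect of 0.50. The adjusted effect is 0.50 / (1 + b²).

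| b | formula | simulation |
|---|---|---|
| 0.25 | 0.50 / 1.0625 = 0.471 | 0.467 |
| 0.50 | 0.50 / 1.25 = 0.400 | 0.399 |
| 0.75 | 0.50 / 1.5625 = 0.320 | 0.320 |

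**4. Entered as one mean per child.** The same adjustment applies to all three of a child's toy-age values and cancels in the within-child difference. I say largely spared because many repeated-measures ANCOVA routines also fit covariate-by-toy-age terms. It does not cancel between children, so age-group comparisons are still adjusted for a post-play outcome.

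**5. Who has a rating.** The three youngest groups (3 × 60 = 180 of 360) have none. The two oldest (2 × 60 = 120) do. In the 36-71 month group, with ages evenly spread, 24 of 36 months lie at or past the fourth birthday: 60 × 24/36 = 40. At most about 120 + 40 = 160 of 360 children (44%) have ratings; if only the two oldest groups are counted, 120 (33%).

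**6. Delay, if liking is asked at the end.** Assume two equal phases and toys spread evenly. Section 4a gives both an hour and 1-2 hours for the play session.
- 60 minutes: phase midpoints at 15 and 45, so mean delays are 60 − 15 = 45 (alone) and 60 − 45 = 15 (with parent).
- 120 minutes: midpoints at 30 and 90, so mean delays are 90 and 30.

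The mean gap is 30 to 60 minutes.

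**7. What delay could do.** Suppose there is no true condition effect and delay alone shifts liking by d_z standard deviations of the within-child difference. A paired two-sided t test at .05 (noncentrality d_z × √n), with 120 to 160 children, rejects in 19-24% of studies at d_z = 0.1, 58-71% at 0.2 and 90-97% at 0.3. The documents give no value for d_z.

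**8. Power.** At N = 360, f = .25 and five covariates, with 3 or 6 repeated measures and correlations from 0 to 0.8, computed power is at least 0.93 in every variant tried. The lowest is the age group by toy age interaction with noncentrality f² × N = 0.0625 × 360 = 22.5 on 10 and 698 degrees of freedom. The .80 in section 10b is met with room to spare.

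**The case against.** The strongest reply is that a covariate in a repeated-measures ANCOVA is usually one value per child. Section 10b counts preference as one covariate and speaks of toys in the plural. On that form the primary within-child contrast is largely untouched. This stands as far as it goes, but section 10a uses both singular and plural and the plan never states the form. Section 10a also allows up to five covariates, so inclusion in every model is not fixed; yet it then lists preference, 10b includes it for both questions, and no rule for leaving one out is given.

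Several stronger readings are tempting and should be resisted:
- A reader might infer that the primary contrast is biased toward zero, by some 10-50%, in all six age groups. Steps 2 and 4 show that this needs per-toy entry and liking that moves with complexity. The percentages come only from assumed slopes, and half the age groups have no ratings.
- A reader might infer that the protocol fixes liking at the end of the session only, and that this timing causes the covariate problem. The timing is read from placement, past tense and a simplified assent script. It is the likeliest reading, and nothing contradicts it, but it is not stated. Step 1 shows that the covariate problem exists at any post-play timing.
- A reader might infer a constant 30-60 minute gap in every child. It is an average; the last alone-phase toy and the first parent-phase toy have almost the same delay.
- A reader might infer that preference is deliberately adjusted for itself. For the 9b outcomes section 10a repeats the independent variables but not the covariates, so a clarifying clause is enough.

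**Conclusion.** The concern holds for the covariate. Preference follows the play, is plausibly a result of age fit, is an outcome in its own right, and exists for fewer than half the children. Entered per toy, it changes what the primary comparison estimates; entered as a child mean, it leaves that comparison largely intact but still enters the age-group comparisons. Direction and size cannot be determined from the documents, and the figures in steps 2 and 3 show only that the effect need not be trivial.

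The delay point is secondary. On the likeliest reading of section 4c, recall delay and condition cannot be separated in the preference contrast, because the alone-first order is the same for every child. Nothing in the documents shows that liking drifts over such intervals, so step 7 is a range of possibilities and not an estimate. It affects only children with ratings and only that one outcome.

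**What to change.** 1. In sections 10a and 10b, remove child preference from the covariates of the main models for both research questions. Keep it as a secondary outcome in 9b, and say that it is not a covariate when it is the dependent variable.
2. If a preference-adjusted analysis is wanted, label it a sensitivity analysis, restrict it to children who have ratings, and state whether preference enters per toy or as a child mean.
3. In section 4c, state when liking is asked. Then either ask about alone-phase toys at the existing switch of phase and parent-phase toys at the end, or state that the alone-versus-parent contrast on preference is confounded with recall delay and order.

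**Cost.** Items 1 and 2 change wording only. The main models may explain slightly less residual variance, which the power margin in step 8 makes easy to accept; one error degree of freedom is regained. Under item 3, asking at the switch splits one question block into two with the same questions in total, but it interrupts the session and could affect parent-phase play. It evens out the average delay when the phases are of similar length; it does not remove the confounding of condition with the fixed order. The disclosure option costs a sentence and limits what can be concluded about preference.
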